## Abstract:

### Background:

Up to 80% of women experience menopausal vasomotor symptoms during the perimenopause transition period, such as hot flashes, night sweats, and flushes, although they can vary between individuals. These often last for more than 7 years for over half of women. These symptoms are related to negative outcomes including depressed mood, reduced social quality of life, and decreased quantity/quality of sleep. A common therapy used to address these symptoms is hormone replacement therapy (HRT), although there is concern with long term use and safety is unknown. Noninvasive, non-drug alternative interventions are needed.

High-resolution, relational, resonance-based, electroencephalic mirroring (HIRREM®) is a closed-loop, allostatic, acoustic stimulation neurotechnology that uses software-guided algorithmic analysis to identify and translate selected brain frequencies into audible tones to support real-time self-optimization of brain activity. Pilot data shows that the use of HIRREM is associated with reduced symptoms of traumatic stress and anxiety, and improved autonomic cardiovascular regulation across heterogeneous cohorts, as well as reduced blood pressure in a small series with comorbid hypertension. This study will evaluate the use of HIRREM for those with hot flashes in a randomized clinical trial.

Objective: The primary objective of this pilot study is to evaluate whether the addition of acoustic stimulation linked to brain activity (HIRREM), to continued current care, will reduce the frequency and severity of vasomotor symptoms experienced by perimenopausal and postmenopausal women.

Methods: This will be a randomized, single site, pilot clinical trial, enrolling up to 40 women, who have at least 5 hot flashes per day (with at least one being categorized as moderate to severe), and who are not taking medications or supplements for management of hot flashes. Participants will be randomly assigned to receive 8-16 sessions over a maximum of 4 weeks of acoustic stimulation linked to brain activity (HIRREM and continued current care, HCC) or will be assigned to a waitlist group (continued current care, CCC). Both groups will continue their other current care throughout. There will be pre- and post-intervention data collection to include physiological outcomes (BP, HR, and measures of autonomic cardiovascular regulation), as well as daily hot flash diaries, Hot Flash Related Daily Interference Scale (HFRDIS), the Menopause Rating Scale (MRS), symptom inventories for insomnia (Insomnia Severity Index, ISI; Pittsburgh Sleep Quality Index, PSQI; and the Epworth Sleepiness Score, ESS), depression (Center for Epidemiological Studies- Depression Scale, CES-D), anxiety (Generalized Anxiety Disorder-7, GAD-7), stress (Perceived Stress Scale, PSS), and a quality of life measure (Quality of Life Scale, QOLS), as well as drop stick reaction testing, and dynamometry for grip strength. Measures will be collected at an enrollment visit (V1). Both groups will then maintain a hot flash diary for 7-14 days, after which the intervention will begin for the HCC group. Post-intervention data collections will be obtained at 4-6 weeks (V2, primary outcome) and 12-14 weeks (V3) following completion of the intervention. Follow up data collection for the CCC group will occur at 10-12 weeks (V2), and 18-20 weeks (V3) after the V1 visit. Both groups will maintain a hot flash diary for 1-2 weeks prior to the V2 and V3 visits. The primary outcome will be differential change in hot flash frequency and severity from

V1 to V2 between HCC and CCC, based on data from the hot flash daily diary. Following V3, those in the CCC group will be offered the opportunity to cross over to receive a course of HCC within 3 months, and will continue to be followed for data collections at 4-6 weeks (V4), and 12-14 weeks (V5) after completing their crossover HIRREM sessions. Additional mean contrasts will be constructed to evaluate the consistency of any benefit of HIRREM through subsequent visits beyond V3. Comparisons of changes in all secondary outcomes will be assessed in a similar fashion.

Importance: This study will explore the use of HIRREM for vasomotor symptoms associated with menopause in a randomized, clinical trial. The study will confirm feasibility using a closed-loop, acoustic stimulation intervention for a randomized clinical trial in this population, and will also provide estimates of effect size, which might justify larger controlled trials. A positive result would suggest that HIRREM might have benefit as a noninvasive, non-drug alternative for management of vasomotor symptoms. This, over and above the potential benefit from participating in a clinical trial, and interacting with the study personnel and the study environment. The study will also help to identify the characteristics of subgroups that might experience differential effects/benefits from HIRREM.

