### Overview:

[figure not shown]
This will be a randomized, single site, pilot clinical trial. Assuming a potential drop-out rate of 20%, up to 48 subjects will be enrolled to achieve a goal of having at least 40 subjects (20 per group) complete the study, per protocol. Patients who have at least 5 hot flashes per day (with at least one being categorized as moderate to severe) will be eligible to participate.

Those who have no other exclusions, are interested to participate, and provide informed consent will be randomly assigned to receive 8-16 sessions of in-office acoustic stimulation linked to brainwave activity (HCC), over a maximum of 4 weeks, while continuing their other current clinical care, or to continue their current clinical care alone (CCC). There will be pre- and post-intervention data collection to include a daily hot flash diary (to be completed for 7-14 days by both groups) and many secondary outcome measures including completion of the MRS, HFRDIS, measures of autonomic cardiovascular regulation (continuous recording of BP and HR for calculation of measure of HRV and BRS), behavioral symptom outcomes (ISI, PSQI, ESS, CES-D, GAD-7, PSS), quality of life measure (QOLS), and function performance measures (drop stick reaction testing, and grip strength). All measures will be collected at an enrollment visit (V1). Both groups will then maintain a hot flash diary for 7-14 days, after which the intervention will begin for the HCC group. Post-intervention data collections will include an intermediate post-intervention visit (V2, primary outcome, 4-6 weeks after intervention completion for HCC, and 10-12 weeks after V1 for CCC), and a final follow up visit (V3, 12-14 weeks following completion of the intervention for HCC, and 18-20 weeks after V1 for CCC). Both groups will maintain a hot flash diary for 1-2 weeks prior to the V2 and V3 visits. The primary outcome will be reduction in frequency and severity of hot flashes score from V1 to V2. Following V3, those in the CCC group will be offered the opportunity to receive a course of HCC within 3 months (will have another brainwave assessment 0-14 days before beginning sessions), and will continue to be followed for data collections at 4-6 weeks (V4), and 12-14 weeks (V5) after completing their HIRREM sessions.

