#### Number of Subjects:

As a pilot study, in a new cohort of participants, using a wait-list control, we are not able to calculate an accurate sample size. In order to evaluate feasibility and effect size, and allowing for up to 20% drop outs, we will arbitrarily enroll up to 48 subjects to achieve a goal of having 40 subjects complete the study per protocol (estimated 20 per group).

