Any collected patient identifying information corresponding to the unique study identifier will be maintained on a separate master log. The master log will be kept secure, with access limited to designated study personnel. Following data collection subject identifying information will be destroyed at the earliest opportunity, consistent with data validation and study design, producing an anonymous analytical data set. Data access will be limited to study staff. Data and records will be kept locked and secured, with any computer data password protected.

Reporting of Unanticipated Problems, Adverse Events, or Deviations:

Any unanticipated problems, serious and unexpected adverse events, deviations or protocol changes will be promptly reported by the principal investigator or designated member of the research team to the IRB and sponsor or appropriate government agency if necessary.

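### The protocol gives two enrolment ceilings, 40 in the abstract and 48 in the body, and 48 falls slightly short of 40 completers at the stated 20% drop-out

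*Combined protocol and SAP*

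**What the plan says.** The number of women to be enrolled appears in three places.

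- **Abstract, Methods paragraph:** "This will be a randomized, single site, pilot clinical trial, enrolling up to 40 women". Neither completion nor drop-out is mentioned in connection with this number.
- **Overview:** "Assuming a potential drop-out rate of 20%, up to 48 subjects will be enrolled", with the aim of "having at least 40 subjects (20 per group) complete the study, per protocol".
- **Number of Subjects:** "allowing for up to 20% drop outs, we will arbitrarily enroll up to 48 subjects to achieve a goal of having 40 subjects complete". This section also says that an accurate sample size cannot be calculated for a pilot in a new cohort with a wait-list control.

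On departures from the protocol, the paragraph on reporting unanticipated problems, adverse events or deviations (under Human Subjects Protection) says that "deviations or protocol changes will be promptly reported by the principal investigator or designated member of the research team to the IRB".

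**The concern.** All three statements have the form of an enrolment maximum, but the abstract's maximum is 40 and the other two are 48. In the body, 40 is a different quantity, the number who finish. The ceiling decides when recruitment stops. The 41st to the 48th woman would be within plan according to the Overview and the Number of Subjects section, but over the limit according to the abstract. Whether her enrolment could be read as a deviation that must be reported to the IRB should not depend on which page is consulted.

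There is a smaller problem with the 48 itself. It is presented as the enrolment that secures 40 completers with a 20% drop-out allowance, and at 20% it does not quite do so.

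**Working it through.** **Inputs**

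- Enrolment ceiling in the abstract: 40.
- Enrolment ceiling in the Overview and Number of Subjects: 48.
- Drop-out: 20% (Overview), or up to 20% (Number of Subjects).
- Completer goal: 40, about 20 per group. The Overview makes this a minimum.
- Alpha, power, effect size and standard deviation: none given, so there is no power calculation to reproduce.

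**Where 48 comes from.** Adding 20% to the completer goal gives 40 × 1.20 = 48, which matches the protocol exactly and is apparently how the figure was obtained. Drop-out applies to those enrolled, however, so the enrolment that yields 40 expected completers is 40 / (1 − 0.20) = 50. The difference is 2 women.

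**The two ceilings compared**

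| | Ceiling 40 (abstract) | Ceiling 48 (body) |
|---|---|---|
| Drop-outs that still leave 40 completers | 40 − 40 = 0 | 48 − 40 = 8 |
| Largest drop-out that meets the goal | 0% | 8/48 = 16.7% |
| Expected completers at 20% drop-out | 40 × 0.80 = 32 | 48 × 0.80 = 38.4 |
| Shortfall against 40 | 8 | 1.6 |

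The gap between the ceilings is 48 − 40 = 8 women. A ceiling of 40 is compatible with a goal of 40 completers only if nobody drops out, and this contradicts the 20% planned for in the body. That is why the abstract's figure looks like the completer goal carried over as the enrolment number.

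**The shortfall with 48.** With equal groups, 24 × 0.80 = 19.2 completers per group against 20, a shortfall of 0.8 per group. The goal is missed from the ninth drop-out onwards (9/48 = 18.75%), a range that includes the stated 20%.

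**Chance of reaching the goal.** As an illustration, suppose each woman drops out independently with probability 0.20. The binomial probability of at least 40 completers is then 0.36 with 48 enrolled and 0.58 with 50.

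**Effect on precision.** If only completers were analysed, and interval width varied as one over the square root of the group size, intervals would widen by √(20/19.2) = 1.02, or about 2%.

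**The case against.** The case on the other side is that this is an editorial slip with little riding on it. The abstract is a summary, while the dedicated section and the Overview agree on 48 and explain how 40 and 48 relate, so a reader can work out what was meant. No test, power statement or estimand depends on the figure. The deviation-reporting paragraph does not say that enrolling the 41st to 48th woman would be a deviation; that turns on the number the IRB approved, which is not in the document. Much of this stands. It limits the seriousness of the conflict, and the reporting consequence is a possibility only. It does not remove the conflict, since an enrolment limit, even an arbitrary one, has to be one number.

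On the shortfall, the Number of Subjects section is worded loosely: it treats 20% as an upper bound, calls the size arbitrary, and describes 40 as a goal. At any drop-out up to 16.7% the goal is met, and 48 is within 2 women of the 50 that the usual formula gives. This makes the point small, but an allowance of up to 20% should still hold at 20%, and the Overview assumes 20% without that qualifier.

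The 2% figure for interval width also deserves caution. The Statistical Analysis section plans linear mixed models, which can use partial data. The primary outcome is described at V2 in the Abstract and Overview, so a woman lost between V2 and V3 is a non-completer who still contributes V2 data. The 2% therefore applies only to a completer-only analysis, and is trivial even there.

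**Conclusion.** The concern holds in both parts.

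- **Main part:** the protocol states two enrolment maxima that differ by 8 women, and no other text reconciles them. That the abstract's 40 is a misplaced completer goal is an inference, though a strong one.
- **Minor part:** at the stated 20% drop-out, 48 enrolled gives 38.4 expected completers against a goal of at least 40. This assumes that the 20% applies to enrolled women and, for the per-group figure, equal allocation.

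Neither part threatens the validity of the trial. The first should be corrected because it concerns a basic design parameter that governs recruitment. The second is an imprecision to put right in the same edit.

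**What to change.** 1. In the Methods paragraph of the Abstract, change the enrolment maximum from 40 to 48, so that it agrees with the Overview and the Number of Subjects section.
2. In those two sections, make the drop-out rate, enrolment and completer number agree. Either state that about 38 completers (about 19 per group) are expected at 20% drop-out, or keep 40 completers and give the allowance as about 16.7% (8 of 48).

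Both steps are wording only and leave the ceiling of 48 in the body unchanged. The cost is that either the expected number of completers or the drop-out allowance is stated slightly less favourably. Raising enrolment to 50 (25 per group) would also reconcile the figures and keep both the 20% and the 40, but it means 2 more women than the body now allows. Given the stated purpose and the small shortfall, that is not necessary.

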## Background:

An estimated 22 million women are between the ages of 45 and 54 years, suggesting that they are entering or have begun the perimenopause transition. Of these women, approximately 75% of them will experience vasomotor symptoms (hot flashes) due to the menopause transition, and 25% will seek medical treatment. Around \$4 billion is spent annually in the United States on medications to treat women going through menopause.

As individuals go through the menopausal transition, their body begins to reduce the production of estrogen and progesterone. Progesterone is a sleep-promoting hormone, so this can also lead to troubles sleeping or even insomnia.

There is evidence that patients are at an elevated risk of coronary heart disease (CHD) when given standard oral doses of hormone therapy treatments, which are often used to manage symptoms associated with perimenopause (Huang, Sawaya, Vittinghoff, Lin, & Grady, 2009). The risk increases for older postmenopausal individuals when compared to those who more recently went through the menopause transition. Due to safety concerns surrounding the use of hormone therapy, there remains a need for safe, effective, relatively brief, non-pharmacological therapies to help manage symptoms in this population.

Autonomic hyperarousal appears to play an etiological role related to vasomotor symptoms associated with menopause. Use of non-pharmacological strategies such as biofeedback and slow abdominal breathing, EMG-biofeedback, and HRV-biofeedback, targeting downstream autonomic function are reportedly associated with improved autonomic function and reduced blood pressure in those with prehypertension (Chen, Sun, Wang, Lin, & Wang, 2016; Innes, Selfe, & Vishnu, 2010; Lin et al., 2012; Wang et al., 2010; Xu, Gao, Ling, & Wang, 2007). Trials of mind-body, relaxation, behavioral, and complementary interventions have shown promise, possibly related to impact on autonomic hyperarousal (Avis, Legault, Russell, Weaver, & Danhauer, 2014; Befus et al., 2018; Guthrie et al., 2018; Innes et al., 2010; Stefanopoulou & Grunfeld, 2017).

High-resolution, relational, resonance-based, electroencephalic mirroring (HIRREM®) was developed by Brain State Technologies, Scottsdale, AZ. It is a commercially available, noninvasive, electroencephalic-based method to facilitate client-unique relaxation and auto-calibration of cortical neural oscillations by reflecting auditory tones in near real time (Gerdes, Gerdes, Lee, & Tegeler, 2013). HIRREM uses scalp sensors to observe brain frequencies and amplitudes in real time, and software-guided algorithmic analysis to identify and translate selected brain frequencies into audible tones to support real-time self-optimization of brain activity. The audible tones are reflected back to the recipient bilaterally, simultaneously, in 4-8 milliseconds, providing an opportunity for the recipient to, figuratively speaking, listen to the song the brain is playing right now. This rapid updating regarding its pattern allows the brain a chance to, self-optimize, self-adjust, “relax,” and reset/get unstuck from what has been stuck stress/trauma response patterns. The brain electrical patterns are typically observed to shift independently, with no conscious, cognitive activity required, no operant conditioning, and no learner in the loop, towards improved balance and reduced hyperarousal.

The mechanism of this effect remains to be fully understood, but may involve resonance between reflected tones and oscillating brain networks, much like a musical instrument tuning itself. Functionally, it may be that this acoustic stimulation facilitates kindling of sleep in neuronal units, which had previously been stuck in the “on” position due to stress responses (Krueger, Huang, Rector, & Buysse, 2013). Better sleep is foundational for all health and healing. A key aspect of observed beneficial effects may also be related to the observed improvement in downstream autonomic function, as evidenced by increased heart rate variability and baroreflex sensitivity, apparently associated with increased dynamic range and flexibility of autonomic responses managed by the brain.

Since 2011, the HIRREM Research Program at WFSM has enrolled over 480 participants in five clinical studies to evaluate the effects and potential benefits of HIRREM. Data have shown reduction in symptoms of insomnia, depression, stress/anxiety, military-related traumatic stress, hot flashes, and persisting symptoms after athletic concussion, associated with the use of HIRREM (C. L. Tegeler et al., 2017). Improved autonomic cardiovascular regulation has also been observed in those receiving HIRREM, including a cohort of adolescents with Postural Orthostatic Tachycardia Syndrome (J. E. Fortunato et al., 2016; J.E. Fortunato et al., 2013; C. Tegeler et al., 2014). In addition, correlation has been reported between high frequency electrical brain pattern asymmetry scores at baseline, and measures of autonomic cardiovascular regulation (C.H. Tegeler, Shaltout, Tegeler, Gerdes, & Lee, 2015).

#### Specific Relevant Pilot Data:

12 women (median age 56 y; range, 46-69 y) were enrolled in an ongoing IRB approved study exploring a variety of neurological, cardiovascular, and psychological conditions, and were identified as also reporting co-morbid perimenopausal symptoms (C. H. Tegeler, Tegeler, Cook, Lee, & Pajewski, 2015). After an initial HIRREM assessment of brain frequencies and amplitudes, baseline data collection included symptom inventories for insomnia (ISI), depression (CES-D), and anxiety (GAD-7), along with physiological and functional measures. Blood pressure and heart rate were continuously recorded while supine, with spontaneous breathing. Participants completed a hot flash diary for a median of 3.5 days (range, 1-11 d) before beginning their HIRREM sessions, and maintained through follow up data collection visits. Subjects then received a median of 13 (range, 8-23) HIRREM sessions approximately 90 minutes each (range, 54-102 min). Sessions consisted of 4-9 protocols, from 6-30 minutes each, with up to two sessions per day, and were received over a median of 9.5 days (range, 4-32 d). All measurements were repeated at the follow-up data collection visit at a median of 10 days (range, 0-20 d) after completing their final HIRREM session.

Primary outcomes included hot flash frequency and severity, sleep and depressive symptoms. High frequency (23-36 Hertz) amplitudes from bilateral temporal scalp recordings were measured at baseline and during serial sessions. Median changes (range, p value) for hot flash frequency and severity were -2.32 (-14 to 3, 0.050) and -1 (-3 to 0.8, 0.004), respectively. Sleep and depression scores decreased by -8.5 (-20 to -1, p = 0.022), and -5.5 (-32 to 8, p = 0.015) points, respectively. Median amplitude in temporal high frequency brain electrical activity was 8.44 microvolts ( $\mu\text{v}$ , 6.27-16.66) at baseline and decreased a median of -2.96  $\mu\text{v}$  (-11.05 to -0.65, p = 0.0005) by the final session.

Table 1: Hot Flashes: Median (Ranges) Scores at Baseline and Final Day of HIRREM Sessions (\*Hot flash score derived by multiplying frequency by worst severity score for each day)

	Baseline	Final Day	Change	P value
Hot Flash Frequency	4.7 (1, 14)	2 (0, 11)	-2.32 (-14, 3)	0.050
Hot Flash Severity	3 (1.2, 4)	2 (0, 3)	-1 (-3, 0.8)	0.004
Hot Flash Score a	9.08 (2, 42)	3.5 (0, 17)	-6.42 (-42, 3)	0.011

Table 2: Changes in clinical category for insomnia after HIRREM based on ISI scores

Clinical Category by ISI Score	Baseline (Percent of Total)	Post-HIRREM (Percent of Total)
No clinically significant insomnia (0-7)	2 (16.67%)	10 (83.33%)
Subthreshold insomnia (8-14)	4 (33.33%)	0
Moderate insomnia (15-21)	3 (25.00%)	2 (16.67%)
Severe insomnia (22-28)	3 (25.00%)	0

Figure 1 (A and B): Figure 1A: Changes in hot flash frequency over time. The Y-axis indicates hot flash frequency. The X-axis indicates the number of days since the start of the HIRREM sessions. Each colored line represents an individual participant in the study. Figure 1B: Changes in hot flash severity over time. The Y-axis indicates hot flash severity (1 = mild, 2 = moderate, 3 = severe, 4 = very severe). The X-axis indicates the number of days since the start of HIRREM sessions. Each colored line represents and individual participant in the study.

[figure not shown]
[figure not shown]

Figure 2 (A and B): Example of observed changes in brain electrical pattern. FFT spectral display of electroencephalic data with frequency (Hz, central Y-axis) plotted against transformed amplitude ( $\mu\text{V}$ , X-axis). Data represents one minute of data from the T3/T4 montage with EC at the baseline assessment (4-A), and at the penultimate minute of the final session (4-B) for one participant, a 47 year old woman. Note the change of amplitudes in the 23-36 Hz range (dark purple color), outlined by red boxes.

